5.2.4.6. Change from Baseline in Frequency of Fecal Incontinence

The weekly fecal incontinence rate for each subject will be computed, as described in [Section 3.3.7](#), for each week of the 4-week treatment period and for the two weeks of the follow-up period. A summary, by treatment group, of the mean weekly fecal incontinence rate, and change from baseline in mean weekly fecal incontinence rate, for each of the 6 study weeks will be presented. The change from baseline in mean weekly fecal incontinence rate will be analyzed using a linear mixed-effects model with fixed effects for gender (stratification variable), treatment, week, the interaction of treatment and week, and the corresponding baseline value; a random intercept for subject will also be specified. The least squares (LS) mean change from baseline will be presented, by treatment groups, and the difference in LS means for each treatment group versus placebo and combined active doses within each age group versus placebo in a separate model for each age group, and overall active doses versus placebo in a separate model with 95% confidence intervals and corresponding statistical p-values.

The baseline fecal incontinence rate will be calculated as the average fecal incontinence rate for each of the two weeks preceding initiation of study drug.

The above analysis will be repeated for the PP Population.

5.2.4.7. Change from Baseline in Frequency and Severity of Defecation Pain

The weekly defecation pain rate for each subject will be computed, as described in [Section 3.3.7](#), for each week of the 4-week treatment period and for the two weeks of the follow-up period. A summary, by treatment group, of the mean weekly defecation pain rate, and change from baseline in mean weekly defecation pain rate, for each of the 6 study weeks will be presented. The change from baseline in mean weekly defecation pain rate will be analyzed using a linear mixed-effects model with fixed effects for gender (stratification variable), treatment, week, the interaction of treatment and week, and the corresponding baseline value; a random intercept for subject will also be specified. The least squares (LS) mean change from baseline will be presented, by treatment groups, and the difference in LS means for each treatment group versus placebo and combined active doses within each age group versus placebo in a separate model for each age group, and overall active doses versus placebo in a separate model with 95% confidence intervals and corresponding statistical p-values.

The weekly average defecation pain score will be determined using the approach defined in [Section 3.3.7](#) and presented for each week in the 4-week treatment period. The change from baseline in the weekly averaged defecation pain score will be analyzed in the FAS Population using a linear mixed-effects model with fixed effects for gender (stratification variable), treatment, week, the interaction of treatment and week, and the corresponding baseline value; a random intercept for subject will also be specified. The least squares (LS) means, with 95% confidence intervals and the corresponding statistical p-value, will be presented for each week, and across all 4 weeks, of the 4-week treatment period for the difference between the difference in LS means for each of treatment group versus placebo, combined active doses within each age group versus placebo, and overall active doses versus placebo. The analysis of interest for this secondary endpoint is the difference in LS means between each plecanatide group (each dose within each age group, combined active dose within each age group, and overall active dose) versus placebo for the estimated overall average change from baseline in defecation pain and defecation pain scores across the 4-week treatment period.

The baseline defecation pain score and rate will be calculated as the average defecation pain score and rate for each of the two weeks preceding initiation of study drug, respectively.

The above analysis will be repeated for the PP Population.

5.2.4.8. Change from Baseline in Frequency of Large Diameter Stools

The weekly large diameter stools rate for each subject will be computed, as described in [Section 3.3.7](#), for each week of the 4-week treatment period and for the two weeks of the follow-up period. A summary, by treatment group, of the mean weekly large diameter stools rate, and change from baseline in mean weekly large diameter stools rate, for each of the 6 study weeks will be presented. The change from baseline in mean weekly large diameter stools rate will be analyzed using a linear mixed-effects model with fixed effects for gender (stratification variable), treatment, week, the interaction of treatment and week, and the corresponding baseline value; a random intercept for subject will also be specified. The least squares (LS) mean change from baseline will be presented, by treatment groups, and the difference in LS means for each treatment group versus placebo and combined active doses within each age group versus placebo in a separate model for each age group, and overall active doses versus placebo in a separate model with 95% confidence intervals and corresponding statistical p-values.

The baseline large diameter stools rate will be calculated as the average large diameter stools rate for each of the two weeks preceding initiation of study drug.

The above analysis will be repeated for the PP Population.

5.3. SAFETY

Values for all safety variables will be listed by subject and visit (as applicable). All safety analyses will be conducted on the Safety Population.

5.3.1. Adverse Events

Adverse events will be mapped to a Medical Dictionary for Regulatory Activities (MedDRA) version 23.0 preferred term and system organ classification. If a subject experiences multiple events that map to a single preferred term, the greatest severity grade (mild, moderate, or severe), and strongest investigator assessment of relation (reasonable possibility, no reasonable possibility) to study medication will be assigned to the preferred term for the appropriate summaries. Should an event have a missing severity or relationship, it will be classified as having the highest severity and/or strongest relationship to study medication. Overall summary of TEAEs will be provided. The occurrence of treatment-emergent adverse events (TEAEs) will be summarized by treatment group using preferred terms, system organ classifications, and severity. Separate summaries of treatment-emergent serious adverse events (SAEs), TEAEs related to study drug, severe TEAEs, and TEAEs leading to the discontinuation of study will be generated using system organ class and preferred terms. All adverse events reported will be listed for individual subjects showing both verbatim and preferred terms. All adverse events that occurred prior to the initiation of study treatment will be excluded from the tables but will be included in the listings.

Missing onset dates will be imputed as previously outlined in [Section 3.3.5](#) as required to determine treatment-emergent events.

5.3.2. Clinical Laboratory Assessments

Laboratory tests (hematology, serum chemistry, and urinalysis) will be summarized as changes from baseline. Laboratory shift tables from baseline to end of study will also be produced. Listings of laboratory tests will also be provided.

Toxicities for clinical laboratory will be characterized according to Common Terminology Criteria for Adverse Events (CTCAE), Version 4.03. Out of range laboratory tests will also be summarized, and a listing of subjects with at least one out of range value will be presented by visit for that test.

Moreover, “Medically Important Events” recently defined by FDA will be reported as SAEs. These include cases where:

- Aminotransferases (ALT or AST) are > 3 times the upper limit of normal (ULN) with an associated elevation of total bilirubin > 2 times ULN without evidence of hemolysis or with alkaline phosphatase < 2 times ULN or not available, or
- ALT or AST activity that is > 5 times ULN

5.3.3. Vital Signs, Height, and Weight

Vital signs will be summarized as changes from baseline. Listings of vital signs will also be provided. A separate listing of subjects with at least one out of range value will be presented by visit for that assessment. The normal range of vital signs is summarized below:

Variable	Units	Normal Range
Systolic blood pressure	mmHg	≤ 120
Diastolic blood pressure	mmHg	≤ 80
Heart Rate	beats/minute	60 to 100
Respiratory Rate	breaths/min	12 to 25
Temperature	°C	< 38

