6.3.1 Individual Patient Stopping Criteria

Adverse events due to study drug that affect individual patient safety may necessitate dose interruptions or early discontinuation as described in this section.

Plecanatide therapy in adults with IBS-C and CIC has caused diarrhea in 4% and 5% of patients respectively, with severe diarrhea occurring in 0.7% and 0.6% of patients respectively. Severe diarrhea may cause dehydration. Pediatric patients may be at increased risk for diarrhea and dehydration with plecanatide therapy.

In general, study drug dosing should not be modified for mild diarrhea (Grade 1: increase of < 4 stools per day over baseline) or mild dehydration (Grade 1: dry mucous membranes, diminished skin turgor) (*National Cancer Institute, Common Terminology Criteria for Adverse Events [CTCAE] v5.0, November 27, 2017*). If study drug is not well tolerated by an individual patient, treatment will be permanently discontinued for that patient.

The following guidelines should be used in the case of moderate or severe diarrhea or dehydration:

Table 4 Individual Patient Stopping Criteria

Worst Observed Toxicity Grade NCI Common Toxicity Criteria	Dose Modification for Study Drug
Diarrhea	
Grade 2: Increase of 4-6 stools per day over baseline	No intervention required
Grade 3: Increase of ≥ 7 stools per day over baseline, incontinence, hospitalization indicated	Interrupt study drug for < 7 days until resolved to less than Grade 2 severity. If diarrhea was study drug-related, permanently discontinue study drug. If diarrhea was not study drug-related, e.g., viral gastroenteritis, then consider resuming treatment after consultation with Sponsor's Medical Monitor
Grade 4: Life-threatening consequences, urgent intervention indicated	Permanently discontinue study drug
Dehydration	
Grade 2: IV fluids indicated < 24 hour	Interrupt study drug for < 7 days until resolved to less than Grade 2 severity. If dehydration was study drug-related, permanently discontinue study drug. If dehydration was not study drug-related, consider resuming treatment after consultation with Sponsor's Medical Monitor
Grade 3: IV fluids or hospitalization indicated	Permanently discontinue study drug

Table 4 Individual Patient Stopping Criteria

Grade 4: Life-threatening consequences, urgent intervention indicated	Permanently discontinue study drug
---	------------------------------------

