8.10 SAFETY ANALYSES

Evaluation of the safety of once daily plecanatide over 4 weeks of dosing will be based on the occurrence of TEAEs, vital signs, and clinical laboratory assessments as compared with those noted in the placebo group.

The safety analyses will use the Safety Population defined in **Section 8.3**.

The frequency of SAEs, AEs leading to withdrawal from study participation, and TEAEs will be included in the primary safety tables.

Adverse events will be coded using the Medical Dictionary for Regulatory Activities (MedDRA) classifications with reference to system organ classes (SOCs) and preferred terms. Only TEAEs will be included in summary tables. Summaries of TEAEs will be presented by SOC and preferred term, by treatment. Summaries will include the frequency of TEAEs, SAEs, and AEs leading to withdrawal from study participation, by dose as well as by intensity and relationship to study drug.

Out of range laboratory tests and vital signs of potential clinical importance will also be summarized; a listing of patients with at least one out of range value will be presented by visit for that test.

Laboratory tests (hematology, serum chemistry, and urinalysis), and vital signs will be summarized as changes from baseline. Laboratory shift tables will also be produced, where applicable. Listings of laboratory tests and vital signs will also be provided.

Physical examination and medical history listings will be provided but not summarized.

Concomitant medications will be auto-encoded using the WHODD coding system with reference to Anatomical Therapeutic Classification (ATC) text and preferred terms. Summaries of concomitant medication will be presented by ATC text and preferred terms. Prior, concomitant, prior and concomitant, and post-treatment medications will be presented separately.

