This is a randomized, double-blind, placebo-controlled, parallel-group study of the efficacy and safety of 4 dose levels of plecanatide (0.5, 1.0, 2.0 or 3.0 mg) in children 6 to < 18 years of age with Irritable Bowel Syndrome with Constipation (IBS-C). Enrollment will be stratified by age group (6 to 11 years in Group A and 12 to < 18 years in Group B). Randomization will be stratified in each Group by gender to ensure gender balance across treatment groups. The study will include a 28-day Screening/Baseline Period, a 4-week Treatment Period, and a 2-week Post-Treatment Follow-up Period. Subjects/caregivers will visit the clinic 4 times during the study.

If a subject is anticipated to turn 12 between screening and randomization, he/she will be randomized into the adolescent group. A subject who turns 12 during the treatment period or post-treatment follow-up period will remain in 6 to 11 years age group.

The overall study plan is presented in [Figure 1](#).

Figure 1 **Study Design**

Screening/Baseline Period: Subjects' legally authorized representatives (e.g., parent/guardian/legally authorized representative) will provide informed consent and subjects, as per IRB guidance, will provide written or verbal assent before they undergo any protocol-specified procedures or assessments. At the Screening visit, subjects will undergo a review of medical history, a review of prior and concomitant medications, a brief dietary history, and a physical examination. During the 28-day Screening/Baseline Period prior to randomization, subjects will record—through an electronic diary—daily assessments of bowel movements (BMs), stool consistency (Bristol Stool Form Scale (BSFS) or Modified Bristol Stool Form Scale for Children (mBSFS-C), and abdominal pain and other IBS-related symptoms. Data from the electronic diary will be used to confirm study

eligibility immediately prior to the randomization visit, as well as to characterize the subject's baseline IBS-C status with which the change from Baseline across and at the end of the 4-week treatment period will be compared.

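### The SAP's blood-pressure range has no lower limit, so the out-of-range listing cannot flag a low pressure, and the summary of out-of-range vital signs promised in the protocol is missing

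*Combined protocol and SAP*

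**What the plan says.** SAP 5.3.3 introduces one table for all subjects with the words "The normal range of vital signs is summarized below". Its limits are:

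- systolic pressure ≤ 120 mmHg
- diastolic pressure ≤ 80 mmHg
- heart rate 60 to 100 beats per minute
- respiratory rate 12 to 25 breaths per minute
- temperature below 38 °C

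These limits drive the out-of-range listing: "A separate listing of subjects with at least one out of range value will be presented by visit for that assessment". SAP 9.3 numbers it 16.2.8.7.2. The other vital-sign outputs are described as follows: "Vital signs will be summarized as changes from baseline. Listings of vital signs will also be provided". They are Table 14.3.5.1.X and Listing 16.2.8.7.1.

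Protocol 8.10 promises more than a listing: "Out of range laboratory tests and vital signs of potential clinical importance will also be summarized". The synopsis likewise promises the proportion of patients with abnormal vital-sign results, and it names significant shifts in vital signs as a safety endpoint.

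On the risk itself, protocol 6.3.1 says "Severe diarrhea may cause dehydration" and "Pediatric patients may be at increased risk for diarrhea and dehydration with plecanatide therapy".

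**The concern.** An out-of-range listing exists to bring individual abnormal readings to a reader's attention. For blood pressure this one works in the high direction only. Low pressure is a possible consequence of fluid loss, and fluid loss through diarrhea is a harm around which the protocol builds both its individual and its study stopping rules (6.3.1 and 6.3.2). The listing would contain no low pressures whatever happened in the trial, and that absence could be taken for a finding.

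The missing summary adds to this. A listing gives no denominators and no counts by dose, which is what a dose-ranging safety comparison needs. Adverse-event reporting does not fully replace it: protocol 7.2 has sites record a diarrhea-type event as an adverse event only if the patient calls it bothersome. That gives an objective measure more value.

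**Working it through.** No sample size, power or event rate enters here, so there is no planned figure to reproduce. The check applies the SAP 5.3.3 table as a flagging rule and then compares promised with planned outputs.

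**Rule as written.** A reading is flagged if systolic > 120, or diastolic > 80, or heart rate < 60 or > 100, or respiratory rate < 12 or > 25, or temperature ≥ 38.

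**Blood pressure.**
- Systolic, whole numbers 0 to 120 (121 values): 0 flagged. The first flagged value is 121.
- Diastolic, whole numbers 0 to 80 (81 values): 0 flagged. The first flagged value is 81.

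**Illustrative patients** (values chosen only to exercise the rule):

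| Blood pressure | Heart rate | Listed? | Reason |
|---|---|---|---|
| 60/30 | 95 | No | No limit crossed |
| 60/30 | 125 | Yes | Heart rate only |
| 80/45 | 100 | No | No limit crossed |
| 80/45 | 101 | Yes | Heart rate only |

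A patient with low pressure is listed only if another variable is out of range or the other pressure is high. Heart rate and respiratory rate in the same table are two-sided, so the format allows lower limits. Neither document gives a low-pressure criterion anywhere else.

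**Promised against planned.**

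| Source | Out-of-range laboratory tests | Out-of-range vital signs |
|---|---|---|
| Protocol 8.10 | Summary and listing | Summary and listing |
| Protocol synopsis | Shifts summarized | Proportion of patients with abnormal results summarized |
| SAP 5.3.2 and 5.3.3 | Summary and listing | Listing only |
| SAP 9.1, summary tables | Toxicity and shift tables | Table 14.3.5.1.X only, by visit |
| SAP 7, changes to planned analyses | Not mentioned | Not mentioned |

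The SAP keeps the out-of-range summary for laboratory tests and leaves it out for vital signs without saying so.

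**How many readings the fix would reach.** The Schedule of Assessments takes vital signs at Visits 1, 2, 3 (or early withdrawal) and 4. Protocol 5.2.2 places the Visit 2 reading before the first dose. Visit 4 is at Day 42, which is 42 − 28 = 14 days after the end of treatment. One scheduled on-treatment reading remains: Day 28 or early withdrawal. Under protocol 5.2.8 the early-withdrawal visit may fall up to 5 days after the last dose.

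**The case against.** The strongest reply is that nothing is hidden. Every reading appears in Listing 16.2.8.7.1. SAP section 5 includes the minimum among its descriptive statistics and calls for both observed values and changes at each time point, so Table 14.3.5.1.X should print the lowest pressure and the largest fall in each group. This stands: what is missing is a flag and a count, not the data. A minimum shows one patient per group, however, and not how many were low.

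Second, dehydration is followed by other routes. Protocol 6.3.1 describes "mild dehydration (Grade 1: dry mucous membranes, diminished skin turgor", and grades worse cases by need for intravenous fluids, hospitalization or threat to life. Blood pressure is not mentioned. Adverse-event tables, stopping criteria and laboratory toxicity tables do not depend on the vital-sign listing. This also stands. The link from low pressure to dehydration is general clinical knowledge, so low pressure can be called only a possible sign.

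Third, timing limits the benefit. Protocol 2.1.5 places severe diarrhea in adults within the first day (IBS-C) or the first 3 days (CIC) of treatment. A scheduled Day 28 reading would seldom coincide with such an event; an early-withdrawal reading might.

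Fourth, protocol section 8 lets the SAP supersede the protocol on analyses. That permits the change, but it does not explain why the change goes unrecorded.

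A reader might go further and infer that the single heart-rate range of 60 to 100 for ages 6 to < 18 is wrong for younger children, or that it causes the gap. The documents support neither. They contain no paediatric reference against which to judge the range, and the gap comes from the missing lower pressure limits alone.

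**Conclusion.** The point holds as a modest gap in safety reporting. As written, the range table classes every low blood pressure as in range, so Listing 16.2.8.7.2 cannot flag one on that variable. Separately, the summary of out-of-range vital signs promised in the protocol is absent from the SAP, and SAP section 7 does not disclose this. Efficacy and power are not affected.

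A reader might infer that hypotension would go unseen, or that the whole pattern of low pressure with fast pulse escapes. Neither follows. Low values remain in the full listing and in the table minima, and a heart rate above 100 is flagged. The pattern that escapes is low pressure with every other vital sign in range. Nor do the documents support a combined criterion of falling systolic pressure with rising heart rate, since they give no thresholds for one.

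The conclusion assumes that the table is complete as it appears in the SAP and that low pressure is of interest as a possible sign of fluid loss. The number of patients affected cannot be estimated from the documents.

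**What to change.** Before unblinding:

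1. Add lower limits for systolic and diastolic pressure to the SAP 5.3.3 table, taken from a paediatric reference that the sponsor names. No values are proposed here.
2. Give the limits by age group (6 to 11 and 12 to < 18), or state why one set serves the whole range.
3. Add a Safety Population table, by dose within age group, counting patients out of range low and out of range high at each post-baseline visit, including early withdrawal. This restores the summary promised in the synopsis and protocol 8.10.
4. Record the revision in SAP section 7.

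The cost is one SAP table and its programming. No new data are needed, since the readings are already scheduled. The gain is limited by the single scheduled on-treatment reading, and the text accompanying the table should say so, so that a low count is not over-read.

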5.3.4. Concomitant Medications

Concomitant medications will be coded using the WHODrug Global B3 March 1, 2020 with reference to Anatomical Therapeutic Classification (ATC) text and preferred terms. Summaries of concomitant medication will be presented by ATC text and preferred terms. Prior, concomitant, prior and concomitant, and post-treatment medications will be presented separately.

5.3.5. Other Safety Analyses

A listing of physical examination findings for all subjects will be provided (where available). Also, frequency summary of 12-lead electrocardiograms at screening for all subjects will be provided.

